5.7.5.5 Main Analytical Approach

An MMRM will be used to estimate the mean change in Centiloid from baseline to Week 116 within each of the substudies. The model will include the change from baseline in Centiloids as the dependent variable, while adjusting for treatment arm (as categorical), visit (as categorical), APOE ε4 status (as categorical; carrier vs non-carrier), type of tracer (as categorical; Florbetaben vs Flutemetamol), baseline Centiloid, baseline Centiloid-by-visit and treatment-by-visit interaction. Visit will be treated as the repeated variable within a participant. An unstructured variance-covariance matrix will be applied to model the within-participant errors; in the case of non-convergence, compound symmetry will be used, together with a robust estimator of standard error (“sandwich” estimator).

In line with the estimand definition, data acquired after the ICE “Substantial reduction in drug exposure due to the COVID-19 pandemic” (as defined in [Table 3](#)) or more than 56 days from treatment discontinuation will be excluded from the analysis and treated as missing for the primary analysis purposes.

There will be no data imputation for missing data. However, the MMRM provides unbiased estimates and valid inference in the presence of missing data, under the MAR (missing at random) assumption.

The difference in least squares means between active drug and placebo arms at Week 116 will be estimated and presented alongside p-value and the 95% confidence interval for treatment difference. A p-value <0.0001 will be regarded as a statistically significant evidence, irrespective of the results of the other primary/secondary endpoints

(along the lines of the [Haybittle–Peto](#) rule, and thus maintaining the overall type-I error within the study).

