The efficacy analyses will be based on the ITT analysis set (see [Table 2](#)) and will compare the active drug arm against the placebo arm with regards to mean change from baseline to Week 116. Two-sided test hypotheses will be defined in the following sections and the type I error level will be 5%. There are two identical Phase III studies, for each respective study the type I error level will be 5%. In order to protect the overall type I error rate (i.e., at each study level) when incorporating the hypothesis testing of multiple endpoints into the analysis, a fixed sequence testing procedure ([Westfall and Krishen 2001](#)) will be used to adjust for multiple comparisons. Testing of each hypothesis will follow a pre-specified order such that an endpoint would only be tested if the preceding one in the hierarchy was significant at 5% alpha level. The endpoint hierarchy, starting with the primary endpoint and including only confirmatory secondary endpoints, is the following:

1. CDR-SB (Clinical Dementia Rating, Sum of Boxes)
2. ADAS-Cog 13 (Alzheimer's Disease Assessment Scale, Cognitive subscale, 13-item)
3. ADCS-ADL (Alzheimer's Disease Cooperative Study, Activities of Daily Living scale) total score
4. FAQ (Functional Activities Questionnaire)

Missing outcome data will be handled using data imputation aligned with the estimand, see [Section 5.3.3](#) for a detailed description of the analysis strategy.

When using a statistical model with baseline covariate adjustment, missing baseline covariate data other than the baseline outcome measure will be imputed to the overall median value for continuous covariates, or will be imputed to the most frequent category for categorical variables. In addition, baseline covariates will be derived from information collected into the eCRF, unless otherwise specified.

In statistical models using change from baseline of a given outcome measure as the dependent variable, there will be no imputation of the baseline outcome value, with the consequence that participants missing the baseline outcome measure will not contribute to the analysis.

The impact of the COVID-19 pandemic on the study and its conduct will be monitored and the overall impact will be assessed and described in the Clinical Study Reports.

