5.4 SECONDARY ENDPOINTS ANALYSES

The same primary estimand's analysis strategy (see Section 5.3.2) will be applied to secondary endpoints listed in Table 5, with the following exceptions for the corresponding estimator:

- *the imputation model will not include, as covariates, the baseline ADAS-Cog 13 total score and the baseline ADCS-ADL total score*

The imputation model will thus include treatment group, visit, and treatment-by-visit interaction, the baseline score and the baseline score-by-visit interaction, and the randomization stratification factors, namely: disease stage, geographic region, the use of AD medication at baseline and the APOE ε4 status

- *the analysis model will not include, as covariates, the baseline ADAS-Cog 13 total score and the baseline ADCS-ADL total score*

The analysis model will thus include treatment, the baseline score and the randomization stratification factors, namely: disease stage, geographic region, the use of AD medication at baseline and the APOE ε4 status

In the following, confirmatory secondary endpoints refer to endpoints included in the type I error control procedure. Other important secondary endpoints not subject to the type I error control procedure are considered as supportive secondary endpoints. For all secondary endpoints, the treatment effect over time will also be considered and the change from baseline to Weeks 24, 52, 76, and 104 will be provided as supplementary analyses.

Table 5 Secondary Endpoints

| Secondary Efficacy Endpoint | Confirmatory | Type |
|---|---------------------|-------------|
| Alzheimer's Disease Assessment Scale, Cognitive subscale, 13-item (ADAS-Cog 13) | yes | Continuous |
| Alzheimer's Disease Cooperative Study, Activities of Daily Living scale (ADCS-ADL) total score | yes | Continuous |
| Functional Activities Questionnaire (FAQ) | yes | Continuous |
| Mini Mental State Examination (MMSE) | no | Continuous |
| Alzheimer's Disease Assessment Scale, Cognitive subscale, 11-item (ADAS-Cog 11) | no | Continuous |
| Coding (Digit Symbol Substitution Test [DSST]) | no | Continuous |
| Verbal Fluency Task | no | Continuous |
| Alzheimer's Disease Cooperative Study, Activities of Daily Living scale (ADCS-ADL) instrumental score | no | Continuous |

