5.7.5.4 Definition of the Estimand for Amyloid PET

The scientific question of interest for the amyloid PET substudies is to assess the effect of the intended study treatment on the PD endpoint, change from baseline in amyloid load burden at Week 116, in the absence of a substantial impact of the COVID-19 pandemic and as if treatment discontinuation would not have occurred.

The primary Amyloid PET estimand is thus described by the following attributes:

- **Target Population:**
Early (prodromal to mild) AD population as identified by the inclusion and exclusion criteria, see Sections 4.1.1 and 4.1.2 of the substudy protocols and Sections 4.1.1 and 4.1.2 of the main study protocols
- **Variable:**
Change from baseline to Week 116 in amyloid PET Centiloid
- **Treatment:**
Prescribed study drug including up-titration to the target dose
- **Population-level summary:**
Difference in variable means between treatment arms
- Intercurrent events
 - Substantial reduction in drug exposure due to the COVID-19 pandemic (defined as ≥ 4 missed dose-months)
 - Treatment discontinuation due to any reason

Amyloid PET is listed in the protocol under “Pharmacodynamic Biomarker Objective”. Considering that Amyloid PET primarily aims at estimating the Pharmacodynamic effect of the drug, rather than a direct measure of clinical efficacy, reporting treatment effect estimated “as if there were no treatment discontinuations and no substantial reduction in exposure due to COVID-19 pandemic” (thus using a hypothetical strategy) addresses the scientific question of interest.

Details for Definition of Variable

The Centiloid variable will be used rather than the original SUVR, because it allows to combine data from different tracers, by mapping SUVR values to a standardized scale. The Centiloid variable is the current common standard in the scientific community.

The primary SUVR measure of interest is computed using a weighted composite target region and whole cerebellum as reference region. The weighted composite target region is composed of (both left and right side):

- frontal lobe,
- parietal lobe,
- temporal lobe lateral,

- cingulum posterior and
- anterior cingulate gyrus

Each region is weighted by its own volume. The Centiloid conversion is a linear transformation of SUVR with tracer-specific parameters that are given below:

Centiloid Equation:

$$CL = \text{SlopeCL} \times \text{SUVR} + \text{InterceptCL}$$

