The simulation results are summarized in [Table 4](#). Simulated type I errors ranged from 4.69% to 5.18% across scenarios and misclassification rates. Simulations based on 10,000 simulated data sets provide a Monte Carlo standard error for type I error estimates of approximately $\pm 0.22\%$. Therefore, these results are fully consistent with strict type I error control at the 5% significance level.

Table 4 Type I Error Rate Estimates for Each of the Scenarios and Misclassification Rates. Simulations are based on 10,000 Simulated Data Sets which Provide a Monte Carlo Standard Error for Type I Error Estimates of Approximately 0.22%.

| Scenario | ICE misclassification rate (from SDCR to NSDCR) | Type I error |
|------------|---|--------------|
| Scenario 1 | 0% | 4.95% |
| | 15% | 4.84% |
| | 30% | 4.97% |
| | 45% | 4.83% |
| Scenario 2 | 0% | 5.11% |
| | 15% | 5.00% |
| | 30% | 5.18% |
| | 45% | 5.13% |
| Scenario 3 | 0% | 4.98% |
| | 15% | 4.81% |
| | 30% | 4.82% |
| | 45% | 4.69% |
| Scenario 4 | 0% | 4.73% |
| | 15% | 4.78% |
| | 30% | 5.00% |
| | 45% | 5.01% |

Conclusion

The primary analysis described in this SAP is based on the method described in [Wolbers et al. \(2022\)](#). This publication describes and justifies the method in detail and provides theoretical and simulation support that it controls type I error.

Clarification and details on the theoretical argument were provided and additional simulations were conducted. These simulations explored plausible scenarios calibrated to the GRADUATE studies. They also assessed the impact of ICE misclassification.

Based on this body of evidence, the proposed method for primary analysis (using conditional mean imputation of missing data combined with the jackknife for inference) adequately controls type I error.

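### Does the separate amyloid-PET claim at p<0.0001 break the 5% type I error that the SAP says is maintained?

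*SAP*

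**What the plan says.** SAP 5.1 controls error study by study: "for each respective study the type I error level will be 5"%, two-sided. All of it goes to a fixed sequence in which "an endpoint would only be tested if the preceding one in the hierarchy was significant at 5% alpha level". The list is described as "starting with the primary endpoint and including only confirmatory secondary endpoints": CDR-SB, ADAS-Cog 13, ADCS-ADL total score and FAQ. SAP 5.4 gives the matching definition: "confirmatory secondary endpoints refer to endpoints included in the type I error control procedure". Protocol 6.4.2 likewise tests the primary endpoint at a two-sided 5%.

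Amyloid PET is not in the list. SAP 5.7.5.4 treats it as a measure of pharmacodynamic effect "rather than a direct measure of clinical efficacy". SAP 5.7.5.5 analyses the Week 116 change in Centiloids separately in each study's substudy and adds: "A p-value <0.0001 will be regarded as a statistically significant evidence, irrespective of the results of the other primary/secondary endpoints". A parenthesis likens this to the Haybittle–Peto rule and concludes "and thus maintaining the overall type-I error within the study".

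SAP 5.8 plans no efficacy interim on the primary endpoint. Protocol 6.7.1 still mentions an O'Brien–Fleming boundary, but SAP section 1 says the SAP takes precedence. No alpha is therefore spent or saved at an interim.

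**The concern.** A fixed sequence run at 5% uses the whole 5%. A further test that can succeed whatever the sequence shows needs its own share of alpha, or the total exceeds 5%. The SAP neither lowers the clinical level to 0.0499 nor reserves 0.0001 elsewhere, so on a strict reading its statement about the overall error is untrue. At stake is whether the stated error control is what the rules deliver, and whether a significant PET result could be reported as confirmatory in a trial that fails on CDR-SB without having been paid for.

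**Working it through.** **Inputs.** Clinical sequence: two-sided 0.05 at every step (SAP 5.1). Amyloid PET: one test per study at 0.0001, not gated (SAP 5.7.5.5). Type I error simulations: 10,000 trials per scenario (SAP Appendix 1). Sample size: placebo change 2.5, 30% reduction, SD 2.97, 90% power, 35% allowance, total 1016 (SAP section 3). The documents give no correlation between the PET and CDR-SB statistics, so the values below are assumptions.

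**1. The plan's own figure.** In a fixed sequence, a false clinical rejection requires rejecting the first true null in the order, which is tested at 0.05. The clinical family therefore has error 0.05, as stated.

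**2. Add the PET test, both nulls true.**
- Union bound: 0.05 + 0.0001 = 0.0501.
- Independent statistics: 1 − 0.95 × 0.9999 = 0.050095.
- Correlated normal statistics, P(|Z1| > 1.9600 or |Z2| > 3.8906):

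| Assumed correlation | Family-wise error |
|---|---|
| 0.1 | 0.050093 |
| 0.3 | 0.050077 |
| 0.5 | 0.050045 |
| 0.7 | 0.050010 |
| 0.9 | 0.050000 |

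The excess over 5% lies between zero and 0.0001.

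**3. When the excess can arise.** It needs a true null for amyloid PET together with a true null in the clinical sequence. If gantenerumab lowers amyloid, a PET rejection is correct and the error returns to 0.05. Protocol 1.3.1 reports mean reductions of 39 Centiloids by Week 52 and 59 by Week 104 in earlier open-label PET substudies. Those data are uncontrolled, but they make a true PET null unlikely.

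**4. Scale.** SAP Appendix 1 says its 10,000 runs "provide a Monte Carlo standard error for type I error estimates of approximately" 0.22%. Check: √(0.05 × 0.95 / 10,000) = 0.00218. Then 0.0001 / 0.00218 = 0.046, about 1/22. The simulated error rates there run from 4.69% to 5.18%. The largest upward departure, 0.18 point, is 18 times the possible 0.01-point excess, and the SAP still regards those results as consistent with strict control.

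**5. What an exact split would do.** First the plan's sample size: the effect is 0.30 × 2.5 = 0.75, the normal approximation gives 330 per arm, and 660 / 0.65 = 1015.4, rounded up to 1016. Now test the sequence at 0.0499 and PET at 0.0001:
- Sum: 0.0499 + 0.0001 = 0.05; if independent, 0.049995.
- Critical z for the clinical tests: 1.9600 becomes 1.9608.
- Power at 330 per arm (1016 × 0.65 / 2): 0.9004 becomes 0.9002.
- Power at 508 per arm: 0.98052 becomes 0.98048.
- Required n per arm: 330 at both levels.

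The split gains at most 0.0001 of error and costs about 0.0002 of power. Neither is of practical size.

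**The case for a change.** The best case for a change is that the SAP speaks of error within the study, not within the clinical family, and that the word *other* before the primary and secondary endpoints sets PET beside them. If PET is in the family, the claim is inexact. If it is outside, the claim is unnecessary. Either way one sentence could be tidied at almost no cost, by calling the PET p-value nominal or by splitting alpha.

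Part of this stands. No alpha is reserved, and a strict threshold makes the excess tiny without making it zero. Anyone who counts PET in the family should read the control as approximate, with a bound of 0.0501.

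The rest does not lead to a change. The study-wide wording allows PET to be placed in the family but does not force it, because SAP 5.1 and 5.4 build the controlled family from the primary and confirmatory secondary endpoints only. The SAP states its level as 5%, and 0.0501 is 5% at that precision. The reference to Haybittle–Peto points to a convention in which a very small threshold is treated as negligible, not to an exact partition of alpha. The remedies also have a price. A nominal label withdraws a PET rule that was prespecified on purpose. A split moves the primary test off the two-sided 5% of Protocol 6.4.2.

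**Conclusion.** The arithmetic behind the concern is right, but no change to the plan follows. Over the confirmatory clinical endpoints the per-study error is exactly 5%. With amyloid PET added to the family it is bounded by 0.0501, and the actual value under a joint null lies between 0.0500 and 0.0501 depending on a correlation the documents do not give. This assumes one PET test per study at the stated threshold and no alpha spent at an interim, as SAP 5.7.5.5 and 5.8 provide. An analyst applying the SAP would reach the same decisions on CDR-SB, on the secondary endpoints and on PET whether or not the parenthesis were reworded. Testing the primary endpoint at 0.0499 would depart from the protocol in order to settle a question of family definition on which statisticians reasonably differ. Leaving the clinical sequence at two-sided 5% and PET at 0.0001 is a fair trade-off.

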5.7.5.6 Supplementary analyses

Changes in weighted Composite Summary region SUVR (for each tracer) and Centiloids from baseline will be summarized using descriptive statistics.

Based on the same model as specified in the Section [5.7.5.4](#), the change from baseline to Week 52 in Centiloids will also be reported as supplementary analysis.

Additionally, the number and proportion of participants with values below or equal to the positivity threshold will be summarized for each assessment time point. Centiloid zero is the mean amyloid burden for a typical population of young healthy controls, and 100 Centiloid is the typical mean of a population with AD. The Centiloid value of 24 is consistent with the diagnostic amyloid positivity threshold ([Klunk et al. 2015](#); [Navitsky et al. 2018](#)) (see Section [5.7.5.3](#) for definition of Centiloid **Error! Reference source not found.**).

A chi-square test (or Fisher’s exact test, whichever is appropriate) will be used to compare the proportions of participants with values below or up to the positivity threshold between the active drug and placebo arm.

In order to account for the potential impact of missing values, a completers analysis will be performed, i.e., restricting the analysis to participants who completed the visit with non-missing data.

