### 3. STUDY DESIGN

#### 3.1 DESCRIPTION OF THE STUDY

##### 3.1.1 Overview of Study Design

This is a Phase III, multicenter, randomized, double-blind, placebo-controlled, parallel-group study designed to evaluate the efficacy and safety of gantenerumab in participants with early (prodromal to mild) AD.

The planned number of participants for the global enrollment phase for the study is approximately 1016 participants randomized in a 1:1 ratio to receive gantenerumab and placebo (508 participants randomized to gantenerumab and 508 randomized to placebo) (see Section 6.1). To maintain a balanced number of participants enrolled in each treatment arm and to ensure that the arms are comparable, randomization will be stratified by stage of disease (prodromal AD vs. mild AD), APOE allele status (presence vs. absence of the  $\epsilon$ 4 allele), use of AD medication (presence vs. absent), geographic region (Western Europe and Australia vs. Rest of the World vs. North America) and participation in longitudinal amyloid and tau PET substudies. Approximately 175 centers in approximately 15 countries worldwide will participate in this study.

Participants will be selected on the basis of clinical diagnosis of probable AD (according to the National Institute on Aging/Alzheimer's Association [NIA/AA] diagnostic criteria and guidelines for AD; see [Appendix 2](#)) (McKhann et al. 2011) or prodromal AD (according to the NIA/AA diagnostic criteria and guidelines for MCI due to AD; see [Appendix 3](#)) (Albert et al. 2011). The aim of the study is to recruit approximately 50% of the participants with prodromal AD.

Eligible participants will be 50–90 years old, inclusive, must show evidence of  $\beta$ -amyloid pathology as indicated by the CSF tau to A $\beta$ 42 ratio (CSF-enrolled participants) or positive amyloid PET scan by visual read (PET-enrolled participants), and meet eligibility criteria as detailed in Section [4.1](#).

The study will consist of a screening period of up to 12 weeks in length following the signing of informed consent. Sites also have the option to prescreen participants on the FCSRT and MMSE. Participants must sign a separate Informed Consent Form before administration of these tests if used for prescreening. If the results confirm a participant's eligibility, then the FCSRT and MMSE will not have to be completed again during the screening period as long as the test has been done within 12 weeks prior the baseline.

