Gantenerumab is an antibody that targets A $\beta$ . Thus, the study population should have documented evidence of amyloid pathology. This participant selection approach is consistent with the NIA/AA research diagnostic criteria and guidelines for AD as well as with the Qualification Opinion from the European Medicines Agency’s (EMA’s) Committee for Medicinal Products for Human Use on the use of CSF biomarkers for enrichment of trials in mild to moderate AD dementia (2012), and the U.S. Food and Drug Administration (FDA’s) draft guidance for early AD (2013). Although the FDA’s guidance refers to the early stage of AD in which individuals present with clinical MCI, biomarkers of amyloid pathology are expected to add value to participant selection in mild AD studies, especially for anti-amyloid treatments (McKhann et al. 2011; Dubois et al. 2014, 2016). Biomarker enrichment is important for anti-amyloid therapy clinical trials because some results of early trials have demonstrated that approximately 20% participants who are enrolled in trials based on a clinical diagnosis of AD alone may not have underlying amyloid pathology as assessed by amyloid PET (Doody et al. 2014; Salloway et al. 2014).

For enrollment in this study, biomarker evidence of  $\beta$ -amyloid deposition will be assessed either by a centralized visual assessment of PET amyloid imaging, using one of the three following amyloid PET imaging tracers (VizamyTM, NeuraceqTM, and AmyvidTM according to country and site availability) or by the CSF tau to A $\beta$ 42 ratio (using a prespecified cutoff and the Roche Diagnostics Elecsys immunoassay).

Both methods (CSF and PET) are established approaches to identify A $\beta$  accumulation in the brain in vivo (Pannee et al. 2016; Vos et al. 2016) and both have been used in research and in clinical practice. There is also emerging evidence that indicates consistency between PET amyloid imaging and CSF biomarkers. Indeed, in biomarker research studies, concordance between amyloid PET and the combination of CSF A $\beta$ 1-42 with t-tau has been shown to be very high with properly controlled CSF methodologies (EMA 2012).

To enrich for participants who are more likely to decline over the 2-year trial, all participants have to demonstrate amnesic deficits as measured by the FCSRT’s total

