- Evidence of AD pathological process, as confirmed by CSF tau/A $\beta$ 42 or on amyloid PET scan by qualitative read by the core/central PET laboratory

- Demonstrated abnormal memory function at screening (FCSRT cueing index  $\leq 0.67$  and free recall  $\leq 27$ )
- Screening MMSE score  $\geq 22$  and CDR-GS of 0.5 or 1.0
- Probable AD dementia (consistent with NIA/AA core clinical criteria for probable AD dementia) (McKhann et al. 2011) or prodromal AD (consistent with the NIA/AA diagnostic criteria and guidelines for mild cognitive decline due to AD) (Albert et al. 2011)
- If the participant is receiving symptomatic AD medications, a stable dosing regimen for at least 3 months prior to screening and until randomization
  - Participants receiving GV-971 or who are planning to take GV-971 during the study are not eligible
- Agreement not to donate blood or blood products for transfusion for the duration of the study and for 1 year after final dose of study drug
- Agreement not to participate in other research studies for the duration of this trial and its associated substudies
- For enrollment in the China extension, participants must have residence in mainland China, Hong Kong, or Taiwan and be of Chinese ancestry.
- For women of childbearing potential: agreement to remain abstinent (refrain from heterosexual intercourse) or use contraceptive methods that result in a failure rate of  $< 1\%$  per year during the treatment period and for at least 16 weeks after the last dose of study drug

A woman is considered to be of childbearing potential if she is postmenarcheal, has not reached a postmenopausal state ( $\geq 12$  continuous months of amenorrhea with no identified cause other than menopause), and has not undergone surgical sterilization (removal of ovaries and/or uterus).

Examples of contraceptive methods with a failure rate of  $< 1\%$  per year include bilateral tubal ligation, male sterilization, hormonal contraceptives that inhibit ovulation, hormone-releasing intrauterine devices, and copper intrauterine devices.

The reliability of sexual abstinence should be evaluated in relation to the duration of the clinical trial and the preferred and usual lifestyle of the participant. Periodic abstinence (e.g., calendar, ovulation, symptothermal, or postovulation methods) and withdrawal are not acceptable methods of contraception.

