| Tau PET modified intent-to-treat (Tau-PET-mITT) | All participants in the ITT analysis set who participated in the Tau PET sub-study and who had at least one Tau PET scan with a valid quantitative measurement and who did not withdraw from the Tau PET substudy before randomization Analysis using this analysis set will be performed by randomized treatment. | All analyses of Tau PET parameters will be based on this analysis set. |
| Tau-PET-longitudinal | All participants in the Tau-PET-mITT with a valid post-baseline quantitative Tau PET measurement. | Summary of treatment group comparability will also be repeated on this analysis set. |

Table 2 Analysis Sets (cont.)

| Analysis set | Definition | Scope |
|---|--|--|
| Amyloid PET modified intent-to-treat (Amyloid-PET-mITT) | All participants in the ITT analysis set who participated in the Amyloid PET sub-study and who had at least one Amyloid PET scan with a valid quantitative measurement performed with either florbetaben or flutemetamol and who did not withdraw from the Amyloid PET substudy before randomization. | All analyses of Amyloid PET parameters will be based on this analysis set |
| Amyloid-PET-longitudinal | Analysis using this analysis set will be performed by randomized treatment. All participants in the Amyloid-PET-mITT with a valid post-baseline quantitative amyloid PET measurement performed with either florbetaben or flutemetamol. | Summary of treatment group comparability will also be repeated on this analysis set. |
| Safety-evaluable | All participants randomized during the global enrollment phase who received at least one dose of study drug. Any participant randomized to placebo who received at least one dose (any dose) of active drug will be summarized as having received the active drug. Analysis using this analysis set will be performed by treatment actually received. | All safety analyses (with the exception of Safety MRI) will be based on this analysis set. |
| MRI Safety-evaluable | All participants in the Safety-evaluable analysis set who had at least one post-baseline safety MRI scan. Analysis using this analysis set will be performed by treatment actually received | All analyses of safety MRI will be based on this analysis set. |

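### SAP 5.7.5.6 compares the proportions at or below 24 Centiloids without regard to baseline, so any participant already there at entry raises both arms' rates and dilutes the difference

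*SAP*

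**What the plan says.** SAP 5.7.5.6 says that "the number and proportion of participants with values below or equal to the positivity threshold will be summarized for each assessment time point". A chi-square or Fisher exact test "will be used to compare the proportions of participants with values below or up to the positivity threshold between the active drug and placebo arm". On the cut-off it says: "The Centiloid value of 24 is consistent with the diagnostic amyloid positivity threshold". The section sets no condition on the baseline value and includes no covariate.

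Three other places bear on who is counted:

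- **Entry.** Protocol 4.1.1 accepts evidence of pathology from the CSF tau/Aβ42 ratio or "on amyloid PET scan by qualitative read by the core/central PET laboratory". Protocol 3.3.1 says the CSF ratio is judged "using a prespecified cutoff and the Roche Diagnostics Elecsys immunoassay". Neither route is a Centiloid criterion.
- **Analysis set.** SAP Table 2 defines Amyloid-PET-mITT as ITT participants in the substudy "who had at least one Amyloid PET scan with a valid quantitative measurement performed with either florbetaben or flutemetamol" who had not left the substudy before randomization. It requires neither a baseline scan nor a baseline above 24.
- **Main PET model.** The repeated-measures model in SAP 5.7.5.5 adjusts for baseline Centiloid, its interaction with visit, APOE ε4 status and tracer. The threshold comparison adjusts for none of these.

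**The concern.** A table of participants at or below a positivity threshold is naturally read as a clearance rate. Protocol 1.3.1 already uses such a figure in that way: it cites 51% below threshold after two years in the open-label studies as support for plaque removal. A participant who starts at or below 24 and stays there counts toward the numerator in either arm although nothing was cleared. Each arm's percentage then combines status at entry with change on treatment, and the difference between arms understates conversion among those who could convert. In a small substudy, a chance difference between arms in the number of such participants also adds noise that the planned test does not remove.

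**Working it through.** The documents give no sample size, power or expected proportion for this comparison, so there is no stated figure to reproduce. What follows is illustrative.

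**Set-up.** Let b be the share at or below 24 Centiloids at baseline, the same in both arms in expectation because of randomization. Let c be the share of baseline-positive participants on active drug who fall to 24 or below. Assume that nobody on placebo crosses the threshold and that nobody already at or below it rises above it.

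- Placebo proportion = b
- Active proportion = b + (1 − b)c
- Difference = (1 − b)c
- Difference among baseline-positive participants only = c

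**A value for b.** Figure 4 in Protocol 1.3.1 gives a baseline mean of 91.1 (SE 9.6, n = 27) for the cohort that had received placebo before the open-label phase.

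- SD ≈ 9.6 × √27 = 49.9
- Share at or below 24 under normality = Φ((24 − 91.1)/49.9) = Φ(−1.34) ≈ 0.09

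This is a rough guide. The scans used florbetapir, whereas this substudy uses florbetaben or flutemetamol. The figure's footnote says the values come from a mixed model, so SE × √n may not recover the raw SD.

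**Effect at b = 0.09, with assumed values of c.**

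| c (assumed) | Active | Placebo | Difference, all participants | Difference, baseline >24 only |
|---|---|---|---|---|
| 0.51 | 0.09 + 0.91 × 0.51 = 55.4% | 9% | 46.4 points | 51 points |
| 0.30 | 0.09 + 0.91 × 0.30 = 36.3% | 9% | 27.3 points | 30 points |

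**Chance imbalance.** The SD of the between-arm difference in the baseline-negative share is √(2 × 0.09 × 0.91/n). With an assumed 50 per arm this is 5.7 points; with 75 per arm it is 4.7 points.

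**Type I error.** In 100,000 simulated trials with b = 0.09 in both arms and no drug effect, the unrestricted chi-square test rejected in 4.8% (50 per arm) and 5.3% (75 per arm).

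**Power, at an assumed 50 per arm.** With c = 0.30, power is 91.6% for all participants and 98.7% when restricted to the expected 45.5 per arm above 24 at baseline (placebo rate set to 0.1% for the calculation). With c = 0.51 both are close to 100%.

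**The case against.** The strongest reply is that the section claims only status, not conversion, and that the randomized contrast is sound. Most of this stands.

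- **Confounding.** A reader might infer that entry status biases the test. It does not. Allocation is 1:1 and stratified by PET substudy participation (SAP 1.2.1), so baseline-negative participants are balanced in expectation and also appear in the placebo proportion. The systematic effect is toward no difference. Chance imbalance is already covered by the test's error rate.
- **Visibility.** SAP Table 7 lists baseline as a time point, so the share at or below 24 at baseline will be tabulated. This helps, but only as a marginal percentage. Missing values are not imputed (SAP 5.7.5.1), so the denominators can differ between visits, and subtracting marginal percentages does not show who converted.
- **Existence.** Nothing supplied shows that this trial has such participants. SAP 5.7.5.4 points to eligibility sections in the substudy protocols, which are not among the documents and could contain a quantitative criterion.
- **Size.** A reader might take larger baseline-negative shares from the other two cohorts in Figure 4. Those cohorts were, or included, patients previously given gantenerumab (Protocol 1.3.1), whom this trial excludes (Protocol 4.1.2.7). A reader might also treat the 51% in Protocol 1.3.1 as a true conversion rate. No baseline-positive denominator is stated there, so it may be the same mixed measure. It serves above only as an assumed value of c.
- **Weight.** The comparison is supplementary and outside the hierarchy in SAP 5.1, and the main Centiloid analysis already adjusts for baseline.

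What remains is that each arm's proportion cannot be read as a clearance rate, and that the planned contrast is diluted if b is above zero.

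**Conclusion.** The point holds as one of interpretation and precision. Because SAP 5.7.5.6 ignores the baseline value, any participants at or below 24 Centiloids at entry raise both proportions and shrink the difference by (1 − b). At the one loosely relevant illustration, b ≈ 9%, the loss is about 5 points from an assumed 51 and about 3 points from an assumed 30. That rests on normality, an SD recovered from a model-based SE, a different tracer, and no crossing of the threshold other than by drug effect. The documents support no claim of confounding, false-positive inflation or a known true difference. They also do not establish b for this trial, which may be zero if the substudy protocol sets a quantitative criterion.

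**What to change.** In SAP 5.7.5.6, report and test the proportion at or below 24 Centiloids among participants whose baseline Centiloid is above 24. Add a baseline-by-visit shift table and keep the all-participants proportion as a secondary summary. Restricting on baseline keeps the randomized comparison intact.

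Alternatively, retain all participants who have a baseline scan and adjust for baseline Centiloid and APOE ε4 status, as the main model in 5.7.5.5 does. Use a penalised or exact method if placebo events are sparse.

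The cost is a wording change and one changed denominator, with no new data. Participants at or below 24, or without a baseline scan, leave the main version of the table, so n is slightly smaller and the headline percentage is lower. If the substudy protocol already requires a baseline above 24 Centiloids, one sentence in the SAP saying so is enough.
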